## Background

The main objective of this study is to compare the effectiveness of 10,600-nm carbon dioxide (C02) fractional laser and 1550-nm non-ablative laser (Fraxel) in the treatment of surgical and traumatic scars as well as identify the minimum number of treatments required to achieve the highest benefit at the lowest cost. This was a split-scar study, so each laser was randomly assigned to half of the scar and then each half of the scar was evaluated separately. Patients assessed scars prior to the first treatment (baseline) and 6 months after the last treatment using the Patient and Observer Scar Assessment Scale (POSAS). At both visits, photographs were taken using identical camera settings, lighting and patient positioning. Four blinded examiners then evaluated these photographs using the Manchester scar scale. There were 100 patients enrolled in the study and of those 83 have POSAS scores for the 6-month follow-up and 84 have photo evaluator scores for the 6-month follow-up (ID LSS108.2 was missing in the patient scores). The data was analyzed using SAS v9.4 software.

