## **Analysis Approach**

First, we looked at the scoring distributions for each photo evaluator to check for differences in scoring patterns. Six paired t-tests were conducted to compare the total scores for all possible combinations of observers for each laser at both time points. Next, to assess the effectiveness of the C02 and Fraxel lasers, five paired t-tests were performed on both the patient self-scores and the photo evaluator scores from the 6-month follow-up:

- 1) C02 laser vs. Fraxel laser at baseline.
- 2) C02 laser vs. Fraxel laser at 6-month follow-up.
- 3) C02 laser at 6-month follow-up vs. C02 laser at baseline.
- 4) Fraxel laser at 6-month follow-up vs. Fraxel laser at baseline.
- 5) Difference in C02 laser after 6 months vs. difference in Fraxel laser after 6 months.

Paired t-tests compare whether the mean of the differences in two paired samples differs from 0. A statistically significant difference would indicate that the average scores are not the same for either the C02/Fraxel lasers or for each laser at different time periods.

We also used McNemar's test to investigate the agreement between the C02 and Fraxel lasers for both the POSAS and photo examiner scores, as well as the agreement between the POSAS and photo examiner scores for the C02 and Fraxel lasers separately.

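### McNemar's test is the only method named for patient-versus-examiner agreement, and it cannot tell good agreement from none

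*SAP*

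**What the plan says.** The last paragraph of the SAP's Analysis Approach gives McNemar's test two jobs. The first compares the lasers within each score set: "We also used McNemar's test to investigate the agreement between the C02 and Fraxel lasers for both the POSAS and photo examiner scores". The second compares patients with examiners within each laser: "as well as the agreement between the POSAS and photo examiner scores for the C02 and Fraxel lasers separately". No kappa, intraclass correlation, limits of agreement or correlation is named for either job.

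The two sources use different instruments. Under Background, patients rated their scars "using the Patient and Observer Scar Assessment Scale (POSAS)", and for the photographs, "Four blinded examiners then evaluated these photographs using the Manchester scar scale". On numbers, Background says that "83 have POSAS scores for the 6-month follow-up and 84 have photo evaluator scores for the 6-month follow-up", so at most 83 patient-examiner pairs exist per laser.

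Elsewhere the scores are compared as means: "Paired t-tests compare whether the mean of the differences in two paired samples differs from 0". Those t-tests compare photo observers with one another, or lasers and time points within a score set. None sets patient scores against examiner scores. The SAP also gives no rule for turning either scale into the categories that McNemar's test needs.

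**The concern.** The method does not answer the question put to it. McNemar's test discards the concordant pairs and tests whether two paired proportions are equal. For patient versus examiner, that means whether one source makes a given call more often than the other. This systematic one-way disagreement is one component of agreement, and it is not enough alone:

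- A non-significant result does not show agreement. Two sources that call improvement equally often, but in unrelated patients, also give it.
- A significant result does not show poor agreement. It shows a one-way difference, which can occur when nearly all pairs agree.

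The study has two outcome sources, patients and blinded examiners. Whether they concur affects how the improvement and superiority hypotheses are read. The only statistic planned for that question cannot support a statement in either direction.

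Laser versus laser is different. There McNemar's test is a valid paired comparison of proportions, and only the label is wrong.

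**Working it through.** The SAP gives no figure for agreement, so there is nothing of its own to reproduce. The only input from it is n = 83 pairs (Background). All cell counts, improvement rates and kappas below are assumptions chosen to show how the test behaves. Pairs are taken as independent and tests are two-sided at 0.05.

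**Formulas.** Let a = both call improvement, b = patient only, c = examiner only, d = neither.

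- Observed agreement: po = (a + d)/n
- Chance agreement: pe = [(a+b)(a+c) + (c+d)(b+d)]/n²
- Cohen's kappa = (po - pe)/(1 - pe), with a large-sample 95% CI
- McNemar chi-square = (b - c)²/(b + c); the exact p-value is binomial on b + c discordant pairs

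The cells a and d do not enter the McNemar statistic.

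**Three constructed tables, n = 83**

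| (a, b, c, d) | po | pe | kappa (95% CI) | McNemar chi-square | exact p |
|---|---|---|---|---|---|
| (21, 21, 21, 20) | 41/83 = 49% | 3445/6889 = 0.500 | -0.01 (-0.23 to 0.20) | 0²/42 = 0 | 1.0 |
| (38, 4, 4, 37) | 75/83 = 90% | 3445/6889 = 0.500 | 0.81 (0.68 to 0.93) | 0²/8 = 0 | 1.0 |
| (38, 8, 0, 37) | 75/83 = 90% | 3413/6889 = 0.495 | 0.81 (0.69 to 0.93) | 8²/8 = 8.00 | 2 × (1/2)^8 = 0.008 |

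Rows 1 and 2 have chance-level and high agreement and the same p-value. Rows 2 and 3 have the same observed agreement and opposite test results. At the extreme, (1, 41, 41, 0) has 1/83 = 1% agreement and kappa -0.98, and still gives p = 1.0.

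**Equal improvement rates.** Rates of 50% to 80% and true kappa from 0 to 0.8 were simulated with 200,000 datasets per scenario. The uncorrected test was non-significant in 94.6% to 95.7% of datasets at every kappa (exact test 96.4% to 99.0%). This is the test's null hypothesis, so a rate near 95% is expected. The result does not move with agreement.

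**Unequal rates, 60% versus 50%.** Here pe = 0.6 × 0.5 + 0.4 × 0.5 = 0.5 and po = 0.5 + 0.5 × kappa. The discordant probability is D = 1 - po, and it splits into (D + 0.1)/2 and (D - 0.1)/2.

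| True kappa | po | Discordant cell probabilities | Significant (uncorrected) | Significant (exact) |
|---|---|---|---|---|
| 0 | 0.5 | 0.30, 0.20 | 25% | 21% |
| 0.4 | 0.7 | 0.20, 0.10 | 40% | 31% |
| 0.8 | 0.9 | 0.10, 0 | 97% | 85% |

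Kappa 0.8 is the maximum for these rates, because the smaller discordant cell is then empty. With a fixed gap in rates, better agreement makes a significant result more likely, the reverse of what a reader told that the test examines agreement would expect.

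**The case against.** The strongest case is about weight, since nothing in the SAP supplies another agreement method.

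- **It is secondary.** Patient-examiner agreement is in neither the objective nor the hypotheses, it comes last in Analysis Approach, and no decision rule hangs on it. The SAP does not say that a non-significant result will be read as agreement. This stands, and it limits the consequence. It does not rescue the method, because no valid statement about agreement can be drawn from the test however it is read.
- **The laser comparison is only a labelling matter.** This stands; that half adds nothing to the seriousness.
- **The equal-rate simulation only restates the test's error rate.** True. The three tables carry the point, and the simulation shows that it holds across rates and kappas.
- **The missing category rule is more basic.** This has force: without a cut-off, the McNemar analysis cannot be reproduced on these two scales. The fix therefore starts there.
- **Kappa has its own weakness.** If most scar halves are called improved, as the first hypothesis expects, kappa can be low and unstable despite high raw agreement. That is a fair caution, and it is why the 2x2 table and observed agreement should be printed beside it. Dichotomising also loses information, which the correlation of change scores partly recovers.
- **The analysis has already been run.** The SAP is written in the past tense, so any cut-off chosen now is post hoc and should be labelled so.

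SAS can print kappa beside McNemar's test, but the SAP does not say that it was requested or reported.

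**Conclusion.** The concern holds. As written, the plan cannot show whether patients and photo examiners agree. At n = 83, the same p = 1.0 arises at 49% and at 90% agreement, and 90% agreement can also give p = 0.008. Those counts and the simulated rates are illustrative, but the conclusion does not depend on them, because the McNemar statistic contains only the discordant cells. It should be fixed, but it does not threaten the main results: the effectiveness t-tests stand apart from it, and for C02 versus Fraxel only the wording is at fault.

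**What to change.** For POSAS versus photo examiner scores, within each laser:

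1. State one common binary call, for example improved versus not improved from baseline in total score, averaging the four examiners first. Label it post hoc.
2. Print the 2x2 table and report observed agreement and Cohen's kappa with a 95% CI. If nearly all halves are called improved, read kappa alongside the raw agreement.
3. Keep McNemar's test beside these only as a check on whether one source calls improvement more often.
4. Report the Spearman correlation, with a 95% CI, of the patient change score with the examiner-averaged change score. Label it association, because the two scales differ.

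For C02 versus Fraxel, describe McNemar's test as a test of difference in the paired proportion improved. Do not read a non-significant result as showing that the lasers agree or are equivalent.

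The cost is a stated dichotomy, revised SAP wording and a few lines of SAS on data already collected.
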